6.2 Medical History

6.2.1 General Medical History

Medical history will be coded using the Medical Dictionary for Regulatory Activities (MedDRA) Version 23.1 or higher. The number and percentage of subjects with any medical history will be summarized overall and for each system organ class and preferred term. Percentages will be calculated based on number of subjects in the safety population.

Subject medical history data including specific details, will also be presented in a listing.

6.2.2 Hematopoietic Cell Transplant History

Hematopoietic cell transplant (HCT) history will be collected at screening and will consist of donor type, cell source, date of transplant, conditioning regimen prior to HCT, diagnosis for which HCT was received, CMV seropositive status, and acute or chronic graft-vs-host disease. HCT history will be summarized in a table by treatment group and overall. Percentages will be based on the number of subjects in the safety population.

HCT history data will also be presented in a listing.

7 Treatments and Medications

7.1 Prior and Concomitant Medications

All medications taken within 1 month of signing informed consent and during the study throughout the end of the study will be collected on the CRF. All medications will be coded according to the World Health Organization (WHO) Drug Dictionary (WHODrug Global-B3 202009 or later).

Prior medications are defined as those medications with a start date prior to the date of first dose of study drug. Concomitant medications are defined as any medications with a start date on or after the date of first dose of study drug or any medications with a start date prior to the date of first dose and a stop date after the date of first dose. Furthermore, a medication could be labeled as both a prior and concomitant medication if it was started prior to the first dose of study drug and continued after the first dose of study drug.

The number and percentages of subjects with at least one prior medication will be summarized by treatment group and overall. The number and percentages of all prior medications will be summarized by treatment group and overall and listed by Anatomical Therapeutic Chemical (ATC) level 2 and preferred term. All summaries will be performed using the safety population.

The number and percentages of subjects with at least one concomitant medication will be summarized by treatment group and overall. The number and percentages of all concomitant medications will be summarized by treatment group and overall and listed by Anatomical Therapeutic Chemical (ATC) level 2 and preferred term. All summaries will be performed using the safety population.

Prior and concomitant medications, including prohibited medication, will also be presented in a listing. Details for imputing missing or partial start and/or stop dates of medications are described in [Section 4.4.2](#).

7.2 Prior and Concomitant Therapies

Prior and concomitant therapies include surgical interventions, procedures, or non-medication treatments (e.g. supplemental oxygen). All reported therapies will be coded using the MedDRA Version 23.1 or higher and classified by system organ class (SOC) and preferred term (PT).

Prior therapies are defined as those therapies with a start date prior to the date of first dose of study drug. Concomitant therapies are defined as any therapies with a start date on or after the date of first dose of study drug or any therapies with a start date prior to the date of first dose and a stop date after the date of first dose.

Both prior and concomitant therapies will be presented in a listing. Details for imputing missing or partial start and/or stop dates of medications are described in [Section 4.4.2](#).

7.3 Study Treatments

The study drug administration data collected from eCRF will be listed.

8 Efficacy and Pharmacokinetics Analysis

Efficacy analysis on LRTC [REDACTED] will be based on ITT population. The efficacy analysis on RSV viral load by RT-qPCR will be based on mITT by RT-qPCR population. The efficacy analysis on RSV viral load by CBIA will be based on mITT by CBIA population. Missing data will not be imputed unless otherwise specified. Relevant subject data listings will be provided to support all efficacy analyses.

8.1 Primary Efficacy Endpoint

The primary endpoint is the proportion of LRTC through Day 28, defined as one of the following, as determined by the Endpoint Adjudication Committee (EAC):

- LRTI by RSV
- LRTI as secondary bacterial pneumonia
- LRTI by unusual pathogens
- LRTC of unknown etiology

The EAC reviewed relevant clinical data and source documentation to determine whether a LRTC occurred, the type and date of onset of any LRTC. Details of the adjudication process were provided to the EAC in an EAC charter. This EAC charter defined the EAC membership, EAC's responsibility, data to be provided to the EAC, review process, documentation of EAC decision, meeting logistics, and meeting frequency.

8.1.1 Primary Analysis

The number and proportion of subjects who developed LRTC through Day 28 will be summarized for each treatment group for ITT population. Subjects with missing LRTC data will be considered having no LRTC event. The LRTC data will also be listed.

8.2 Secondary Efficacy Endpoints

8.2.1 RSV viral load AUC by RT-qPCR from Baseline (Day 1) through Day 49

The RSV viral load will be measured in nasopharyngeal swabs by quantitative RT-qPCR at the following scheduled visits: Days 1, 4, 7, 11, 16, 21, 28, and 49. Viral load values reported as TD (Target detected) are samples with viral RNA concentrations equal and above the LOD (limit of detection) ($TD \geq LOD$) and below the LLOQ (lower limit of quantification). ($TD < LLOQ$). For analysis purpose, TD will be set to the average of LOD and LLOQ. Viral load values reported as TND (Target Not Detected, value below LOD) will be set to zero. Viral load data will be transformed using a \log_{10} scale before analyses. If zero values are observed, the log transformed value will be set to zero. For the RT-qPCR assay used for detection and quantification of RSV A and RSV B, the LLOQ is 1000 copies/mL for RSV A and 250 copies/mL for RSV B and the LOD is 620 copies/mL for RSV A and 80 copies/mL for RSV B.

The RSV type of each subject will be decided at baseline based on the RT-qPCR test. The baseline RSV by RT-qPCR result is from the nasopharyngeal swab sample taken after randomization and prior to first dose on Day 1. After the imputation of TD, TND, and \log_{10} transformation, if the baseline RSV A viral load is greater than RSV B viral load, the baseline RSV type is classified as RSV A. And if the baseline RSV B viral load is greater than RSV A viral load, the baseline RSV type is classified as RSV B.

After the categorization of baseline RSV type, only RSV values from the same baseline RSV type will be selected for postbaseline values to be used for analyses.

The AUC of RSV viral load by RT-qPCR will be calculated using the trapezoid rule ([Matthews et al., 1990](#)). To calculate AUC, at least two non-missing data points on the RSV by RT-qPCR curve are needed. The AUC will be calculated based on available individual assessments of viral

load collected at each visit (Days 1, 4, 7, 11, 16, 21, 28, and 49) and the actual date/time of each assessment will be used for the calculation. For the baseline viral load (Day 1), time is set as 0. For each assessment post first dose, the actual time in days is computed as difference between the date/time of the assessment and the date/time of the first dose. The AUC is also standardized to 49 days by multiplying $49/t_{last}$ where t_{last} is the actual time in days of the last available assessment up to Day 49 visit.

[figure not shown]
The descriptive statistics for the RSV viral load AUC by RT-qPCR from Day 1 to Day 49 will be presented by treatment group based on the mITT by RT-qPCR population. The RSV viral load by RT-qPCR data will be listed.

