3.2.2 Secondary Endpoints

- Change in RSV RNA viral load from Baseline through Day 49 in nasopharyngeal swab samples by RT-qPCR
- Incidence of subjects with RSV RNA viral load below the limit of detection in subjects receiving EDP-938 through Day 49
- Plasma PK concentrations of EDP-938
- Safety endpoints include, but are not limited to, adverse events (AEs), serious adverse events (SAEs), vital sign measurements, pulse oximetry measurements, and clinical laboratory test results (including chemistry, hematology, and urinalysis)

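### A subject positive for both RSV A and RSV B at baseline can be counted as below the limit of detection while the other type is still detected

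*SAP*

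**What the plan says.** SAP 8.2.1 gives the RT-qPCR assay separate limits for the two types: LOD 620 and LLOQ 1000 copies/mL for RSV A, and LOD 80 and LLOQ 250 copies/mL for RSV B. After imputation and log10 transformation the higher baseline value decides the type: "if the baseline RSV A viral load is greater than RSV B viral load, the baseline RSV type is classified as RSV A", and the reverse for B. From then on, "only RSV values from the same baseline RSV type will be selected for postbaseline values to be used for analyses".

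The AUC is defined in the same section. Change from baseline (8.2.2) and the by-visit proportion below LOD (8.2.3) follow it. Neither section restates or lifts the restriction, and 8.2.3 does not say whether both types must be undetected.

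The endpoint in SAP 3.2.2 is "Incidence of subjects with RSV RNA viral load below the limit of detection in subjects receiving EDP-938 through Day 49". Protocol 2.2.2 words it the same way. Neither names a subtype. The RSV subgroup categories in SAP 6.1 are A, B, undetectable and missing, with no category for both. The visible text of SAP 12 does not list the restriction among the changes to the planned analysis.

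**The concern.** The endpoint asks whether RSV RNA is gone. The derivation asks whether the type that was higher on Day 1 is gone. The two questions have the same answer for a subject with one type only. For a subject with both types they can differ, and the derivation then reports clearance in someone who is still shedding RSV. The same truncated series feeds the AUC and the change from baseline, so all three viral-load summaries shift towards apparent success. With no category for both types in the baseline table, a reader of the summary tables could not see that this had happened.

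**Working it through.** The SAP prints no figure for this point, so there is nothing to reproduce. The check applies its rules as written.

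**Inputs from SAP 8.2.1.** The limits are those given above. For a result detected but below the LLOQ (TD), "TD will be set to the average of LOD and LLOQ". For a result not detected (TND), "Viral load values reported as TND (Target Not Detected, value below LOD) will be set to zero", and "If zero values are observed, the log transformed value will be set to zero". Scheduled swabs on Days 1, 4, 7, 11, 16, 21, 28 and 49 correspond to t = 0, 3, 6, 10, 15, 20, 27 and 48 days.

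**Step 1: what the rule does over time.** The record below is hypothetical (log10 copies/mL). Baseline A exceeds baseline B, so the subject is typed A.

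| Day | 1 | 4 | 7 | 11 | 16 | 21 | 28 | 49 |
|---|---|---|---|---|---|---|---|---|
| A (kept) | 5 | 4 | 3 | TND | TND | TND | TND | TND |
| B (discarded) | 4.5 | 4.5 | 4.5 | 4.5 | 4.0 | 3.5 | 3.0 | TND |
| Larger of the two | 5 | 4.5 | 4.5 | 4.5 | 4.0 | 3.5 | 3.0 | 0 |

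Trapezoid AUC, A only: 3(5+4)/2 + 3(4+3)/2 + 4(3+0)/2 = 13.5 + 10.5 + 6 = 30 log10-days.

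Trapezoid AUC, larger of the two: 14.25 + 13.5 + 18 + 21.25 + 18.75 + 22.75 + 31.5 = 140 log10-days.

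The SAP's standardization multiplies each by 49/48, giving 30.6 and 142.9. The ratio does not change. Days 11, 16, 21 and 28 are scored below LOD while B is at 4.5, 4.0, 3.5 and 3.0.

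A milder hypothetical record gives a smaller gap. Take A at 10^6, 10^5, 10^4, 2000, TD, then TND, and B at 10^5, 10^5, 30000, 10000, 3000, 1000, TD, TND. The standardized AUC is 68.8 for A only against 129.0 for the log10 of summed copies. Two visits are scored below LOD with B still detected: Day 21 (B at 1000) and Day 28 (B at TD).

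**Step 2: weight of one subject.** One subject moves an arm's by-visit proportion by 100/n points. The SAP gives 9 randomized at 2:1 but not the actual split. At an assumed 6:3 the shift is 100/6 = 16.7 or 100/3 = 33.3 points. For n = 7 to 5 it is 14.3 to 20.0 points, and for n = 4 to 2 it is 25.0 to 50.0 points. The mITT by RT-qPCR population excludes subjects undetectable or missing at baseline, so n may be smaller than the randomized arm.

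**Step 3: does the TD imputation distort the baseline type?**

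- TD becomes (620+1000)/2 = 810 for A and (80+250)/2 = 165 for B, so two TD results are always typed A.
- A at TD means 620 to under 1000, and B at TD means 80 to under 250. The lowest A exceeds the highest B, so type A is the true order. Setting TD to LOD, LLOQ, LLOQ/2, LOD/2 or the geometric mean for both types also gives A.
- With A at TD and B quantified at 250 to 620, A is again truly the higher.
- Misordering by imputation is possible only with A at TD and B at about 620 to 1000, a band of log10(1000/620) = 0.21. Below 810 the error is towards A, and above 810 it is towards B.
- The higher LOD for A works the other way: a true A load just under 620 is TND, set to zero, and loses to B at TD.

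**The case against.** The strongest defence is that following the baseline type is a choice of estimand. It tracks the predominant infection present at entry, and the rule is written down in advance. That has force for a second type first detected after baseline, since whether a new infection should count against treatment is debatable. It does not cover a subject who enters with both types, because the endpoint is RSV RNA and the SAP nowhere calls it type-specific.

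The practical defence is that little depends on it. SAP 12 drops the tests and treatment comparisons, only 9 subjects were randomized, and the RT-qPCR data are listed. This stands and limits the weight of the point.

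A reader might infer more than the documents support:

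- *The unequal TD values bias low-level dual detections towards A.* Step 3 shows they do not: the TD/TD order is correct, and the narrow band of possible misordering runs both ways.
- *The AUC becomes zero.* It cannot. The kept type is positive at time 0, and only later contributions vanish.
- *The rule shows that dual positives occurred.* It does not. Each subject has an A and a B result, so a series must be chosen even when only one type is present.
- *The rule favours EDP-938.* Protocol 1.3.1 reports EC50 values of 21 and 23 nM for two RSV A strains and 64 nM for the RSV B strain. A falling while B persists is therefore conceivable on active drug, but this is in vitro evidence and does not establish a direction of bias.

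**Conclusion.** The point holds for subjects with both types detected at baseline. Read as written, 8.2.1 and 8.2.3 count such a subject as below LOD once the kept type is TND, whatever the other type shows, and the AUC and change from baseline leave out the remaining virus. This is a stated rule that gives the wrong answer for the stated endpoint.

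The size is conditional. No effect arises if no subject had both types at baseline, and the documents give no count. One affected subject would move an arm's proportion by about 17 or 33 points under the assumed 6:3 split. The AUC contrasts come from invented trajectories and show what the rule can do, not what is expected. The check also assumes that both results exist at post-baseline visits. The selection rule implies this, but the SAP does not say so outright.

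**What to change.** In SAP 8.2.1 and 8.2.3, for subjects with both types detected at baseline:

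- define below LOD as TND on both the A and the B result at that visit;
- derive viral load at each visit as log10 of the summed A and B copies/mL (or the larger of the two), with the existing TD and TND values, and use it for the AUC and change from baseline.

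Keep the baseline type as a descriptor only, assigned by the existing higher-value rule. Do not let a quantified result outrank a TD result: for B at 250 to 620 with A at TD, that would reverse a correct order. Flag in the listing any second type first detected after baseline.

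Subjects with only one type detected throughout are unchanged. The cost is a few sentences and a small amount of extra derivation from results the baseline rule already draws on. Protocol 11.1 bars SAP changes after unblinding. If that has happened, a note in the clinical study report and a flagged listing of dual-positive subjects would serve.

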8.2.2 Change from Baseline in RSV viral load by RT-qPCR over time

Observed and change from baseline values for RSV viral load by RT-qPCR will be summarized with descriptive statistics by visit (Days 1, 4, 7, 11, 16, 21, 28, and 49) for each treatment group based on mITT by RT-qPCR population and will include the number of non-missing measurements, mean, standard deviation, median, minimum, 25th percentile, 75th percentile, and maximum.

8.2.3 Proportion of subjects with RSV viral load by RT-qPCR below the LOD over time

The proportion of subjects with RSV viral load by RT-qPCR below the limit of detection (LOD) will be summarized by visit (Days 4, 7, 11, 16, 21, 28, and 49) for each treatment group based on mITT by RT-qPCR population.

[REDACTED]

[REDACTED]

[REDACTED]

8.4 PK Endpoints

8.4.1 Plasma PK concentrations of EDP-938 [REDACTED]

On Day 1, Day 7, and Day 21, two samples will be collected: one predose, collected within 1 hour before dosing (preferably within 30 minutes of dosing if possible); and at the same approximate time as that of the nasopharyngeal swab collection and one postdose, collected 1 to 3 hours postdose. At all other visits (Days 4, 11, and 16), one predose plasma PK sample will be collected at the same approximate time as that of the nasopharyngeal swab collection. Time and date of collection will be recorded on the Plasma PK Sample Collection eCRF.

For subjects in the PK analysis set, the concentration data for EDP-938 and each [REDACTED] will be summarized by visit (Days 1, 4, 7, 11, 16, and 21) and timepoint (predose or postdose). Concentrations that are below the limit of quantitation (BLQ) will be treated as zero for the computation of descriptive statistics. If more than 50% of subjects have concentration values below BLQ, descriptive statistics will not be presented except for maximum and BLQ will be displayed for mean and minimum. The number of observations, arithmetic mean, SD, % coefficient of variation (%CV), median, minimum, maximum, geometric mean, and %CV of the geometric mean (%GCV) will be displayed.

Individual data will be presented in a listing.

9 Safety Analysis

All safety analyses will be conducted using the Safety (SAF) population, where subjects will be analyzed according to the treatment actually received.

9.1 Adverse Events

Adverse events (AEs) will be coded using the MedDRA Version 23.1 or higher and classified by SOC and PT.

AEs will be classified as pre-treatment AEs and treatment emergent adverse events (TEAEs) and are defined as follows:

- A pre-treatment event is any event that meets the criteria for an AE/SAE and occurs after the subject signs the ICF but before receiving the first administration of study drug.
- A TEAE is defined as an AE occurring or worsening on or after the date of first dose of study drug.

A treatment-related AE will be defined as related if causality is related or possibly related. AEs where the causality is missing will be assumed to be related in table summaries.

TEAEs leading to study drug discontinuation will be identified as TEAEs with a study drug action taken of “Drug Withdrawn”. TEAEs leading to death will be identified as TEAEs with an outcome of “Death Related to Adverse Event”.

Adverse events (serious and non-serious) will be graded in accordance with the NCI-CTCAE scale as follows: Mild (Grade 1), Moderate (Grade 2), Severe (Grade 3), Life threatening (Grade 4), and Death (Grade 5). AEs with missing severity will be assumed to be severe in table summaries.

Details for imputing missing or partial start and/or stop dates of AEs are described in [Section 4.4.2](#).

All summaries of AEs will be based on treatment-emergent adverse events (TEAEs) in the safety population. The following summaries of TEAEs will be provided by treatment group:

- An overall summary of TEAEs including the number of TEAEs and the number and percentage of subjects with any of the following: TEAEs, study drug related TEAEs, TEAEs of grade 3 or higher, TEAEs by maximum grade, TEAEs leading to study drug discontinuation, TEAEs leading to death, serious TEAEs, and study drug related serious TEAEs.
- TEAEs – by PT and SOC
- Study Drug-Related TEAEs - by PT and SOC
- TEAEs of Grade 3 or Higher - by PT and SOC
- TEAEs by Maximum Grade – by PT and SOC
- TEAEs leading to study drug discontinuation – by PT and SOC
- AEs leading to death – by PT and SOC
- Serious TEAEs – by PT and SOC
- Study Drug-Related Serious TEAEs – by PT and SOC

For the above summaries by SOC and PT, each subject is counted once within each unique category. For the summary by maximum severity, subjects who experience the same event several times, with different severity levels, will only be counted with the maximum severity.

AEs will be sorted in descending order of frequency of SOC based on the total of all treatment groups. Within each SOC, AEs will be sorted in alphabetical order of preferred terms.

Subject AEs will also be presented in a listing.

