9.2.1 Documenting and Reporting Adverse Events

All AEs reported from the time of informed consent to the EOS visit for each subject will be recorded in the subject's source documents. For subjects who do not receive study drug (ie, alternates or screen failures), AEs will only be recorded in the source documents. For subjects enrolled into the study (ie, randomized), all AEs will be recorded in the subject's AE eCRF and the SAE form (if applicable). The site should record all AEs regardless of the intensity, seriousness, or relationship to study drug.

Adverse events (serious and nonserious) will be graded in accordance with the NCI-CTCAE scale as follows:

- **Mild** (Grade 1): asymptomatic or mild symptoms; clinical or diagnostic observations only; intervention not indicated
- **Moderate** (Grade 2): minimal, local or noninvasive intervention indicated; limiting age-appropriate instrumental activities of daily living

- **Severe** (Grade 3): severe or medically significant but not immediately life-threatening; hospitalization or prolongation of hospitalization indicated; disabling; limiting self-care activities of daily living
- **Life threatening** (Grade 4): life-threatening consequences; urgent intervention indicated
- **Death** (Grade 5): death related to the AE

Any recurrence of an AE with similar causality to study drug will be reported as recurrence or exacerbation of the initial event, and not as a new event. Whenever possible, AEs will be reported as a specific diagnosis or syndrome (eg, flu syndrome) rather than as individual signs or symptoms. If no specific diagnosis or syndrome is identified, AEs should be reported as separate and individual events.

An AE includes the following:

- Progression or exacerbation of the subject's underlying disease. Clinical sequelae that result from disease progression, such as pleural effusion or small bowel obstruction, are reportable as AEs
- Pre-existing event that increases in frequency or intensity
- Condition detected or diagnosed during the study period, even though it may have been present, in retrospect, before the first dose of study drug
- Laboratory abnormalities outside of normal limits with associated clinical symptoms or suspected latent clinical symptoms in the opinion of the Investigator, including those requiring therapeutic intervention

The following events will not be identified as AEs in this study:

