9.2.4 Classifying Adverse Event Outcome

For every AE/SAE, the possible outcomes of the event and the definition of the outcome are shown in [Table 3](#). One outcome must be entered into the appropriate field on the AE and (if appropriate) SAE form for each event.

Table 3: Classification and Definition of Adverse Event Outcomes

Classification	Definition
Recovered/resolved	Resolution of an adverse event with no residual signs or symptoms
Recovered/resolved with sequelae	Resolution of an adverse event with residual signs or symptoms
Is Recovering/is resolving	Incomplete improvement to date but adverse event continues to improve/resolve and complete resolution is expected over time
Not Recovered/not resolved	Either incomplete improvement or no improvement of an adverse event, such that it remains ongoing
Fatal	Outcome of an adverse event is death. "Fatal" should be used when death is at least possibly related to the adverse event
Unknown	Outcome of an adverse event is not known (eg, a subject lost to follow-up)

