9.5 Electrocardiogram

All subjects will have a standard 12-lead electrocardiogram (ECG) performed locally during the study at Screening, Day 4, Day 11, Day 21, and Day 28.

ECG data includes heart rate, RR interval, PR interval, QRS duration, QT interval, and QT interval corrected for heart rate according to Fridericia (QTcF), etc.

ECG data for subjects will be presented in a listing.

10 Interim Analysis

No interim analysis was conducted.

11 Data Monitoring Committee (DMC)

An independent Data Monitoring Committee (DMC) was established to review the safety data throughout the study to ensure the safety of study subjects, the ethical continuation of the study, and provide recommendations regarding continuation or termination of the study. The DMC was headed by a DMC Chair and will include one or more physicians with expertise in transplant medicine. The DMC consisted of experts independent from the Sponsor.

The roles, responsibilities and rules governing operation of the DMC were discussed in full in the DMC charter, which was finalized prior to the administration of investigational product. The DMC charter defined the primary responsibilities of the DMC; guide its activities, its relationship with other study components, its membership, and the purpose and timings of its meetings. It provided the procedures for ensuring confidentiality, formal communication, and outline of the content of reports that will be provided by the DMC.

12 Changes in the Planned Analysis

The study was terminated early by sponsor on September 12, 2023. Due to the small number of subjects randomized into the study, it was decided a reduced data analysis will be provided. The statistical tests or large sample-based estimates defined in the protocol, such as Cochran Mantel-

Haenszel (CMH) test p-value, 95% CI for proportions, treatment difference estimates in proportions and its 95% CI, Cox proportional model estimate for hazard ratio and its 95% CI, Kaplan-Meier estimates will not be provided for treatment comparison purpose. The study exposure duration and compliance will not be calculated. The incidence of treatment-emergent laboratory tests, vital signs, or ECG will not be summarized. The summary of observed and change from baseline in vital sign and ECG will not be provided.

[REDACTED]

In addition, the following endpoints defined in the protocol are deleted from this analysis plan. If the related raw data will still be listed, some details are provided as needed:

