- Incidence of subjects who develop respiratory failure of any cause requiring mechanical ventilation (invasive or noninvasive) or all-cause mortality through Day 49
 - Respiratory failure events requiring mechanical ventilation can be identified based on the Concomitant Therapy eCRF where the response to the respiratory failure therapy question is Yes. Death events can be identified based on the Adverse Events eCRF where the outcome is checked as “Fatal” and/or severity as “Death”. The mechanical ventilation will be listed. The all cause mortality will be listed in AE listing.
- Time to RSV RNA viral load below the limit of detection
- Plasma PK concentrations of EDP-938 in relation to the following:
 - RSV RNA viral loads from Baseline through Day 49
 - [REDACTED]
- Incidence of subjects hospitalized or rehospitalized through Day 49
 - Hospitalization data will be listed. A subject will be considered being hospitalized or re-hospitalized if the subject has any hospitalization or re-hospitalization that starts or restarts on or after the first dose date.
- Incidence of medically attended acute respiratory infection (MAARI) through Day 49
 - The MAARI data will be listed. A subject will be considered as developing MAARI if the subject has any hospitalizations, home health visits, non-hospitalization visits, or receives any concomitant therapies related to MAARI that occur on or after the first dose date. The dates of the medical visits and therapy use related to MAARI were collected on the Hospitalization eCRF, Home Health Care Visit eCRF, MAARI Non-Hospitalization Visit eCRF, and the Concomitant Therapy eCRF, respectively.
- Incidence, duration and number of days free of supplemental oxygen requirement through Day 49
 - A subject will be considered as requiring supplemental oxygen if the subject was administered any supplemental oxygen on or after the first dose date. Dates of supplemental oxygen use were reported on the Concomitant Therapy eCRF. The available supplemental oxygen data will be listed.
- Duration of time of hospital stay and time in the ICU through Day 49
- Incidence of use of certain therapeutics including antibiotics, ribavirin, corticosteroids, and/or immunoglobulin through Day 49

- The data for individual subjects who use certain therapeutics through Day 49 will be included in the concomitant medication listing.
- Emergence of EDP-938 resistance-associated variants (RAVs) in RSV obtained from nasopharyngeal swab samples

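### SAP 9.1 flags fatal TEAEs by an outcome value absent from the protocol's outcome list and at odds with SAP Section 12, so the death summaries could read zero after a death

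*SAP*

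**What the plan says.** SAP 9.1 defines the fatal-event flag by one condition on the outcome field: "TEAEs leading to death will be identified as TEAEs with an outcome of" *Death Related to Adverse Event*. Two planned outputs concern TEAEs leading to death: a line in the overall TEAE summary, and the table "AEs leading to death – by PT and SOC".

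The protocol describes the outcome field differently. Section 9.2.4 requires that "One outcome must be entered into the appropriate field on the AE and (if appropriate) SAE form for each event", and Table 3 lists the possible entries. The one for death is *Fatal*, defined as "Outcome of an adverse event is death".

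SAP Section 12 gives a second rule, under the respiratory failure or all-cause mortality endpoint: "Death events can be identified based on the Adverse Events eCRF where the outcome is checked as" *Fatal*, and/or the severity is *Death*. It adds that "The all cause mortality will be listed in AE listing".

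SAP 9.1 also retains TEAEs by maximum grade (in the overall summary and by preferred term and system organ class), TEAEs of Grade 3 or higher, and serious TEAEs. Its grading scale has Death as Grade 5. An adverse event with missing severity is counted as severe.

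**The concern.** The SAP has two rules for recognizing a death, and they disagree. The one that governs the death summaries names a value that neither Protocol Table 3 nor the SAP's own account of the case form contains.

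The phrase in 9.1 resembles the protocol's definition of severity Grade 5 in Section 9.2.1, "death related to the AE". Wording for a severity grade may have been carried into a rule about outcome, although the documents do not confirm how it arose.

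At stake is the accuracy of the outputs that a reader opens first to learn whether anyone died. Protocol 11.7.1 makes adverse events leading to death a minimum item of the safety summary. A zero there that is an artefact of the selection rule would misstate the gravest safety outcome.

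**Working it through.** The point involves no sample size, power or alpha figure, and the plan gives no figure to reproduce. The check compares the rule with the permitted values and then applies it to invented records.

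**Step 1. Compare the 9.1 value with the permitted outcomes.** Table 3 lists Recovered/resolved; Recovered/resolved with sequelae; Is Recovering/is resolving; Not Recovered/not resolved; Fatal; Unknown.

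- Matches to *Death Related to Adverse Event*, ignoring case: 0 of 6.
- Matches to *Fatal*: 1 of 6.

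**Step 2. Is the 9.1 phrase meant as a form value?** The sentence just before it identifies TEAEs leading to discontinuation by the action *Drug Withdrawn*. That is an exact entry in Protocol Table 2, apart from capitalization. The sentence on death has the same construction, so the natural reading is that it too names a form value.

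**Step 3. Apply each rule.** Take 9 subjects with one TEAE each, k of them fatal and recorded as outcome *Fatal*, Grade 5. The other 9 − k are non-fatal. The counts are illustrative.

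| k fatal TEAEs | SAP 9.1 flag | Section 12 rule | Grade 5 row |
|---|---|---|---|
| 0 | 0 | 0 | 0 |
| 1 | 0 | 1 | 1 |
| 2 | 0 | 2 | 2 |
| 3 | 0 | 3 | 3 |

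The 9.1 flag is right only when k = 0. For any k above 0 it disagrees with the Grade 5 row, and since the overall summary carries both items, the contradiction would sit inside one table.

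**Step 4. One fatal TEAE with outcome *Fatal* and no grade.** SAP 9.1 treats missing severity as severe, which is Grade 3 on its scale.

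| Output | Count |
|---|---|
| SAP 9.1 flag | 0 |
| Section 12 rule | 1 |
| Grade 5 row | 0 |
| Grade 3 or higher | 1 |

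Here no summary identifies the event as a death. It is counted as a Grade 3 event, and only the AE listing would show the fatal outcome.

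**The case against.** The strongest reply is that this is a label slip with little practical reach. Table 3 reserves *Fatal* for deaths at least possibly related to the adverse event, so the 9.1 phrase means much the same thing, and a competent programmer would map one to the other. The case form is not among the documents, so the claim that the field lacks the 9.1 value is an inference from Table 3 and Section 12. A zero count also requires literal matching, with no mapping and no cross-check. With 9 subjects, a conflict with the Grade 5 row or the listing would be hard to overlook. All of this is fair. It makes the harm conditional, but it does not reconcile the two rules, and a final SAP should not depend on a programmer choosing the right one.

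A reader might go further and infer that the SAP has stripped out the other outputs that would reveal deaths, because Section 12 says that "the following endpoints defined in the protocol are deleted from this analysis plan" and the list includes respiratory failure or all-cause mortality through Day 49. The documents do not support that:

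- The maximum-grade summaries keep Death as Grade 5, and all-cause mortality stays in the AE listing.
- Serious TEAEs are still tabulated, and Protocol 9.1.3 makes any event resulting in death serious.
- The deleted endpoint was a composite with respiratory failure, so it would not have isolated deaths.
- The deletion is disclosed, with its reason: early termination and few subjects randomized. Restoring a summary row for it would be a preference, even though the matching objective still stands in SAP 2.2.

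**Conclusion.** Wrong as written. The 9.1 value matches none of the six Table 3 outcomes and contradicts Section 12. Read as a form value, it would miss every fatal TEAE, and two outputs would be affected: the leading-to-death line and the leading-to-death table.

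This rests on two assumptions: that the outcome field on the form carries the Table 3 values, as Section 12 indicates, and that the rule is programmed as it stands. The documents do not say whether any subject died. They therefore support the statement that these outputs could be false, not that they are.

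Two other inferences should be avoided. Expressing a missed death as a percentage of an arm is unsupported, since SAP 4.1 gives only the total of 9 and no arm sizes. The protocol's 21% to 83% mortality range does not indicate how many deaths to expect, because it concerns patients with LRTI, and inclusion criterion 7 requires no new imaging evidence of LRTI at entry.

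**What to change.** In SAP 9.1, replace the sentence on death with: *TEAEs leading to death are TEAEs with outcome Fatal and/or severity Death (Grade 5).* This is the Section 12 definition, so one rule would then apply throughout. In the Step 3 illustration it returns 0, 1, 2 and 3, and in Step 4 it returns 1.

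Add a programming check that the leading-to-death line and table agree with the Grade 5 row and the AE listing, and query any event with outcome *Fatal* whose grade is missing or below 5.

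The cost is one sentence and one reconciliation check, with no new data. Protocol 11.1 does not allow SAP changes after unblinding. If that has already happened, the definition actually applied should be stated in the study report.
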